Full title:

A Multicenter Randomized Controlled Trial Assessing the Efficacy of Antimicrobial Prophylaxis for Extracorporeal Shock Wave Lithotripsy on Reducing Urinary Tract Infection

Brief Title:

Antibiotic Prophylaxis Before Shock Wave Lithotripsy (APPEAL)

1. Objectives & Specific Aims

The lifetime risk of developing nephrolithiasis has been reported between 1-15%, with a prevalence of approximately 5% in North America. SWL is a very common first line treatment for ureteral and renal calculi. One of its benefits is that it has few complications. However, infection remains an important complication of the procedure. Because of this risk the American Urological Association recommends pre-SWL antibiotics for all patients. However, this approach is controversial because studies to date are of poor quality and there is concern over antibiotic resistance. Therefore the European Association of Urology recommends only selective use of antibiotics pre-SWL. To resolve this conflict and establish the most appropriate strategy for Ontarians, we propose to perform a randomized trial comparing pre-procedure antibiotics to no antibiotics among patients who undergo SWL.

The primary goal of our study is to evaluate the impact of antibiotic prophylaxis on the rate of bacteriuria, symptomatic UTI, pyelonephritis and urosepsis among patients with sterile urine undergoing SWL. Our secondary goal is to determine pre-procedural characteristics that can define patient subgroups with the greatest benefit from prophylactic antibiotics.

We hypothesize that a single dose of intravenous ciprofloxacin immediately prior to SWL will decrease the relative incidence of bacteriuria, symptomatic UTI, pyelonephritis and urosepsis by 60% or greater. Additionally, we anticipate that pre-operative patient and stone characteristics such as age, gender, history of UTI, patient comorbidities, stone size, location, may be predictive risk factors that can be used to optimize patient selection for pre-operative antibiotic use.

To test this hypothesis we propose to conduct a large ($n \geq 1350$), multicenter prospective randomized, blinded, placebo controlled trial (RCT). We recognize that our primary question may be difficult to study due to low rates of symptomatic UTI post-SWL. Therefore we propose to undertake this RCT in two phases. The Vanguard phase, which will consist of up to one fourth of the total study population, will be used to determine feasibility. Feasibility will be assessed in terms of rates of patient recruitment, percent adherence to randomization, percent data completion and percent loss to follow-up. Using pre-defined criteria, if the study is deemed to be feasible without major protocol alterations, the Vanguard phase patients will be included in the larger study. Patient recruitment will then continue until our target population size has been reached. Should the Vanguard phase be unable to demonstrate feasibility, then the available data will be analyzed, which will still provide the largest and most methodologically robust dataset available in the literature at this time.

The results of our RCT, whether positive or negative, will contribute significantly to the existing literature as it will provide the strongest Level 1 evidence available for future meta-analyses and guidelines. If the study results show a benefit to antibiotic use the expected impact on patient care will be to reduce rates of infectious complications. Furthermore, our study will allow for a more selective use of antibiotics as several important predictors of infectious complications will be elucidated through a multivariate analysis. Conversely, a null study will provide the strongest evidence against routine prophylaxis in the literature to date and potentially decrease the unnecessary use of antibiotics among patients undergoing SWL. Consequently, this would represent a cost savings to the healthcare system and may reduce the risk antibiotic resistant bacteria.

2. Background, Rationale & Present State of Knowledge

The lifetime risk of developing nephrolithiasis has been reported between 1-15%¹⁻³, with a prevalence of approximately 5% in North America⁴. Recent reviews suggest that the incidence and prevalence of kidney stones are increasing globally^{5,6}. Extracorporeal shock wave lithotripsy (SWL) is a preferred treatment for the majority of renal and ureteric calculi⁷⁻⁹. One significant advantage of SWL is the relatively low rate of complications. However, infectious complications are among the most common, even among patients with sterile pre-SWL urine cultures. The reported rate of bacteriuria is 8-23%^{10,11}, symptomatic urinary tract infection (UTI) is 1.4-5.7%^{12,13} and urosepsis is 0.1-2.7%^{10,11}. These reports have led to considerable interest in the use of prophylactic antibiotics prior to SWL. The American Urological Association (AUA) has recently published a Best Practice Statement on antimicrobial prophylaxis and recommended antibiotic prophylaxis for all patients undergoing SWL, even those with sterile urine. This position was based on evidence from a meta-analysis published by Pearle et al in 1997¹³. In contrast, a more recently published review by Bootsma et al.¹⁴ and a meta-analysis by Lu¹⁵ concluded that there was no role for antibiotic prophylaxis for uncomplicated patients undergoing SWL. This position is further supported by the European Association of Urology (EAU) Guidelines, which recommend selective antibiotic prophylaxis, only for patients with indwelling catheter, nephrostomy tube, or infectious stones^{16,17}.

The AUA Best Practice Statement on the use of perioperative antibiotics for urological procedures relies heavily on a single meta-analysis published in 1997^{13,18}. In their meta-analysis, the results of eight prospective RCTs (n=885)¹⁹⁻²⁶ and six clinical series (n=597)²⁷⁻³¹ were analyzed. The authors concluded that the use of antibiotic prophylaxis prior to SWL for patients with sterile pre-treatment urine cultures reduces post-SWL UTI rates and may be cost effective. Unfortunately, these trials were highly heterogeneous. The heterogeneity was not formally quantified or accounted for by the authors. All eight RCTs used different antibiotic regimens, lengths of follow-up and definitions of bacteriuria and UTI. Many of the antibiotic regimens used were not common urological practice and are of questionable generalizability^{23,25,26}. Additionally, the meta-analysis included two RCTs in which the prophylactic arm received a seven day course of antibiotics and a third trial in which a 48 hour regimen was used^{20,22,23}. This in particular may be of concern as the AUA Best Practice Statement recommends antibiotic prophylaxis for 24 hours or less based on this meta-analysis¹⁸. In our study, we propose to test the standard of a single pre-procedure dose of intravenous ciprofloxacin versus placebo.

Since the publication of Pearle *et al.*'s meta-analysis, there have been two additional RCTs investigating the use of prophylaxis for SWL^{32,33}. Beirkens et al. attempted to perform a five arm single blinded RCT, comparing single dose ciprofloxacin 200mg IV, single dose cefuroxime 750mg IV, ciprofloxacin 200mg daily for seven days, Cefuroxime 750 mg on day one and 250 mg for six days, and placebo. A total of 177 patients were recruited (30/41/39/29/38 per group respectively). However, the study was ended after interim analysis failed to reveal any significant difference between placebo and antibiotic groups. Their results show a non-significant difference in symptomatic UTI between antibiotic and placebo groups of 2.0% vs. 3.0% at two weeks, and 1.4% vs. 2.7 % at six weeks. This study could conceivably have addressed important questions regarding the optimal regimen of prophylaxis. Unfortunately, the power of this study to find potential benefit for any given regimen is limited due to the relatively rare occurrence of UTI post-ESWL and the small sample size for the number of treatment arms. A second study by Ghazimoghaddam et al. attempted to randomize 150 patients into 3 arms (septran, nitrofurantoin, no antibiotic). The authors identified rates bacteriuria of 10-14% in each group at two weeks post-SWL and concluded that prophylaxis did not seem to be necessary. Unfortunately this study was also significantly underpowered in particular for a three arm trial³³. Our proposed study design will avoid this problem by limiting the study groups to prophylaxis

vs. placebo and we propose to recruit a sufficiently large sample size ($n \geq 661$ per arm) to detect a 60% relative decrease in incidence of infectious complication with a power of 90% and a $p=0.05$.

In a recent systematic review of antibiotic use in urologic procedures, Bootsma et al. performed a review of four RCTs regarding antibiotic prophylaxis for SWL¹⁴. These included three from Pearle *et al.*'s meta-analysis^{19,21,24} and the study by Beirkens *et al.*³². The authors excluded two studies^{22,23} as these evaluated 7 day antibiotic treatment regimens rather than prophylaxis. An additional two studies^{25,26} were excluded due to incomplete description of methodology and inconsistency between results and conclusions. A small RCT²⁰ ($n=49$) was excluded but not commented on by the authors. It is likely that this study did not meet inclusion criteria as it mandated a 48hour antibiotic regimen pre-op and defined bacteriuria as $>10^4$ CFU/ml. In their synthesis of the remaining data Bootsma et al. concluded that the available evidence was of low quality and routine antibiotic prophylaxis was not indicated in SWL.

More recently, a formal meta-analysis of 9 studies was carried out by Lu et al¹⁵. This meta-analysis included the three trials^{19,21,24} common to previous analysis, three trials^{20,22,25} which had been excluded from the review by Bootsma et al. and three additional trials^{33,34,35}. It is unclear why the authors chose to include the trials previously excluded by Bootsma et al., as each had significant methodological flaws such as incomplete description of methodology²⁶, 7-day treatment course of antibiotics²³. It is equally unclear why other trials with similar methodological problems were not included^{24,27}. Of the three additional studies, one was new³³ and the other two had either been excluded or not captured in the previous reviews and meta-analysis. In the analysis by Lue et al., the authors report pooled risk ratios with a test of heterogeneity for fever, positive urine culture both (short-term <7 days and mid-term >7 days) and symptomatic urinary tract infection and the presence of double-J stent separately. The I^2 values for these parameters were 60% for fever, 37% and 49% for short-term and mid-term bacteriuria, 0% for UTI, and 0% for presence of double-J stent. We caution that the I^2 value for the latter two parameters does not imply perfect homogeneity between studies, but is an artifact of the low number of events in any given study. Overall, the variability among I^2 values indicates that there is considerable heterogeneity among studies included in their meta-analysis. Nonetheless, the authors fail to find benefit for antibiotic prophylaxis. Notably, the authors of all 3 reviews and meta-analyses on the topic acknowledge the poor quality of available studies and suggest the need for a large high quality randomized controlled trial.

Despite the poor quality of evidence available, the EAU guidelines on urological infections and on urolithiasis regarding the use of antibiotic prophylaxis for SWL recommend antibiotic prophylaxis only for patients perceived to have increased risk of bacterial burden. These are defined as those with an indwelling catheter, nephrostomy tube, or infectious stones. Therefore, to account for these plausible recommendations, our proposed study will exclude patients with indwelling catheter, nephrostomy tubes or known, or suspected, struvite stones.

Based on the existing literature, a prominent area of concern that emerges is how to define a positive urine culture and how to assess for symptomatic urinary tract infection. Previous studies have used a variety of bacterial concentration cutoffs for the definition of a positive culture¹³. We will use the most common historically accepted definition ($\geq 10^5$ CFU/ml) to define a conservative estimate of bacteriuria for the primary and secondary endpoints of our study³⁶. To define a symptomatic UTI we will capture symptoms in two different ways. We will use a predefined questionnaire in a systematic way asking patients to identify both the presence and absence of lower urinary tract symptoms as well as to quantify the magnitude of these symptoms on a scale from 0 to 5. We recognize that the passage of stone debris or presence of stent can cause lower urinary tract symptoms, but believe that appropriate randomization over a sufficiently large cohort will control for this confounder.

In addition we will evaluate the IPSS score as a quality of life measure for lower urinary tract symptoms post-SWL. We believe this is important as symptoms of UTI related to SWL may worsen IPSS scores and correlate to decreased quality of life. It is therefore of benefit to evaluate whether pre-operative antibiotic use can impact on this aspect of patient care. Unfortunately there have not been any systematically validated questionnaires that can be used to diagnose urinary tract infections among men and women. The urinary tract infection symptom assessment questionnaire (UTISA) has been validated to track resolution of UTI symptoms among symptomatic women. However it is not diagnostic nor has it been validated in men³⁷. We have chosen to use the IPSS, as it has been widely validated for the description of lower urinary tract symptoms in men³⁸⁻⁴⁰. It IPSS has also been frequently used to define lower urinary tract symptoms in women in several clinical contexts⁴¹⁻⁴⁴. We recognize that it has not been shown to be useful in the evaluation of bladder outlet obstruction in women⁴⁵, a pathology that we are not assessing in our RCT.

3. References

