The proposed study will be carried out in two phases. The initial Vanguard phase will assess the feasibility of the trial in terms of rates of patient recruitment, percent adherence to randomization, percent data completion and percent loss to follow-up. Pre-defined criteria to determine feasibility will be a rate of randomization of ≥ 16 patients per week, with 95% adherence to randomization and an overall rate of $\geq 90\%$ data collection at 3 weeks post-SWL, and an overall loss to follow-up of $\leq 10\%$. These parameters will be assessed weekly throughout the Vanguard period. This phase of the study will continue until all target parameters have been met for 3 consecutive weeks and a minimum of 200 patients have been randomized. If these parameters are met then the Vanguard phase will be interpreted to have demonstrated feasibility and patient recruitment will continue until complete data for ≥ 1350 patients has been collected. Alternatively, the Vanguard phase may be concluded when a maximum of 300 patients or a six month period from study start date has elapsed or a modification to number of sites accruing may be considered. If the Vanguard phase fails to demonstrate feasibility, and we judge that this indicates that a significant protocol modification is needed we will close the trial and analyze available data. The data would be analyzed in accordance with pre-defined methodology and would be submitted for publication. Importantly, even if the Vanguard phase does not show feasibility, it would still provide the largest cohort of high quality data available in the literature and as such would still be an important contribution to the current state of knowledge.

The study centres, Helsinki University Hospital, University of Western Ontario St Joseph's Hospital, Université de Sherbrooke, Pontifical University Catholic of Campinas, Rede D'Or Sao Luiz, and King Abdulaziz University are each academic institutions with dedicated research staff. We estimate that total of 2000 patients will need to be screened in order to acquire complete data for 1350 patients. Accounting for a 10% dropout, up to 1500 patients may need to be randomized. Eligibility criteria include patients older than 18 years presenting for SWL who do not meet one of the pre-defined exclusion criteria. Exclusion criteria are:

- Pre-SWL urine analysis positive for nitrites
- Pre-SWL urine culture reveals $>10^5$ CFU/ml of bacteria (positive urine culture)

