The power calculation for this protocol was performed using Stata v.10.1 (StataCorp, College Station, TX). Reported incidence of bacteriuria, symptomatic UTI and pyelonephritis post-SWL vary greatly¹⁰⁻¹³. Therefore, to estimate the expected incidence of our primary outcome, we used the incidence of bacteriuria reported in the AUA Best Practice Statement on antibiotic prophylaxis¹⁷. In the AUA statement, patients undergoing SWL in the placebo arm of trials assessing antibiotic prophylaxis had a 5.7% rate of bacteriuria as compared to 2.1% among those who received prophylaxis. This represented an absolute difference of 3.6% (a 60% relative risk reduction). Therefore to achieve a power of 90% to find an absolute difference of 3.6% in the occurrence of bacteriuria, with a significance level of $p < 0.05$, 661 patients will need to be recruited in each arm for a total of 1,322 patients. Accounting for 10% loss to follow-up, the total required will be 1454, or approximately 1500 patients. Assuming that 25% of patients screened will either refuse to be randomized or will meet one of the pre-defined exclusion criteria, a total of 2000 patients will need to be screened in order to randomize 1500 patients.

Statistical analysis

Once all study data has been collected, we will report the patient characteristics at enrollment, and the primary and secondary outcomes. Comparison between RCT outcomes will be performed using Fisher's exact test for binary outcomes and Student's t-test for continuous outcomes. Lost to follow-up will be accounted for according to intent to treat analysis. Patients who are lost to follow-up will be considered not to have bacteriuria, cystitis, pyelonephritis or urosepsis and a change in IPSS of zero. This will allow us to accomplish the primary objective: to determine the impact of antibiotic prophylaxis on our primary and pre-defined secondary endpoints. We will also perform a univariate and multivariate analysis using a stepwise logistic regression model to assess predictors of our primary

outcome. This will allow us to better characterize the impact of pre-SWL antibiotic use in the context of other known risk factors for UTI.

Strengths and weaknesses of study design

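### A null result is expected to count against routine prophylaxis, but the plan pre-specifies no interval for the treatment effect and no benefit to be ruled out

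*Combined protocol and SAP*

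**What the plan says.** - **Intended reading of a null result.** The last paragraph of section 1 says "a null study will provide the strongest evidence against routine prophylaxis in the literature to date" and adds that this could reduce antibiotic use. The closing paragraph of Strengths and weaknesses of study design expects the results to affect recommendations whichever way they fall.
- **Hypothesis.** Section 1 expects that prophylaxis "will decrease the relative incidence of bacteriuria, symptomatic UTI, pyelonephritis and urosepsis by 60% or greater". This is a superiority hypothesis.
- **Sizing.** Power and sample size calculation uses a "5.7% rate of bacteriuria as compared to 2.1% among those who received prophylaxis" and sets out "to achieve a power of 90% to find an absolute difference of 3.6% in the occurrence of bacteriuria", which gives 661 per arm. The recruitment target in section 4 is complete data on at least 1350 patients.
- **Analysis.** Statistical analysis says: "Comparison between RCT outcomes will be performed using Fisher's exact test for binary outcomes and Student's t-test for continuous outcomes". A stepwise logistic regression follows, but its stated purpose is to find predictors of the primary outcome. Neither the subsection nor the rest of the document plans a confidence interval for the treatment effect, a margin, or a smallest worthwhile benefit.
- **Early closure.** If the Vanguard phase shows the trial is not feasible and a major protocol change is needed, section 4 says "we will close the trial and analyze available data", using the pre-defined methods, and submit the result for publication.

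**The concern.** Failing to reject at the 5% level shows lack of benefit only if the data also exclude a benefit worth having. The plan describes an important use for a null result but provides no tool to tell an informative null from an uninformative one.

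The protocol makes a closely related criticism of others. Section 2 faults a three-arm trial of 150 patients for concluding that prophylaxis seemed unnecessary when it was underpowered, and raises a similar power objection to a five-arm trial of 177 patients. This trial is much larger, but it is powered for a large effect. A moderate true benefit could give p>0.05 and be cited against prophylaxis. At stake is what the trial may conclude in one of its two main scenarios.

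**Working it through.** **Inputs.** Control rate 5.7%, prophylaxis rate 2.1%, power 90%, alpha 0.05 (Power and sample size calculation). 675 per arm is 1350/2 (section 4). The control rates of 10% and 15% are assumptions. They fall within the 8-23% that section 2 reports for bacteriuria alone. The 5.7% is itself a bacteriuria rate, whereas the primary endpoint also counts symptoms.

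**1. The plan's own figure.** With mean rate p̄ = 0.039 and a two-sided test:

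n₀ = [1.960·√(2·0.039·0.961) + 1.282·√(0.057·0.943 + 0.021·0.979)]² / 0.036² = (0.8860/0.036)² = 605.6

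With continuity correction: n = (n₀/4)·[1 + √(1 + 4/(n₀·0.036))]² = 660.03, rounded up to **661**. The stated size reproduces. The effect it covers is 1 − 2.1/5.7 = 63% in relative terms (the protocol says 60%). Exact Fisher power for this effect is 91.7% at 661 per arm and 92.0% at 675.

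**2. What null results can look like.** 5.7% of 675 is 38.5; take 38 control events. The interval for the risk difference is Newcombe's: upper limit = d + √[(u₁−p₁)² + (p₂−l₂)²], where l and u are Wilson limits for each arm. For 38 versus 23: p₁ = 5.630% (Wilson 4.129 to 7.633), p₂ = 3.407% (2.281 to 5.061), d = 2.222.

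- Upper limit: 2.222 + √(2.003² + 1.126²) = 4.52
- Lower limit: 2.222 − √(1.501² + 1.654²) = −0.01
- Risk ratio: 23/38 = 0.605, standard error of the log 0.2585, 95% CI 0.365 to 1.005

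| Control vs prophylaxis events (of 675) | Fisher p | Risk difference, points (95% CI) | Excludes 3.6? |
|---|---|---|---|
| 38 vs 23 | 0.066 | 2.22 (−0.01 to 4.52) | No |
| 38 vs 27 | 0.203 | 1.63 (−0.68 to 3.98) | No |
| 38 vs 30 | 0.384 | 1.19 (−1.18 to 3.58) | Just |
| 38 vs 38 | 1.000 | 0.00 (−2.50 to 2.50) | Yes |

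38 versus 22 gives p=0.047, so 38 versus 23 is the largest non-significant benefit with 38 control events.

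**3. How often a real benefit gives p>0.05.** Exact power is the sum, over all pairs of event counts, of the product of the two binomial probabilities, keeping pairs with Fisher p≤0.05. At 675 per arm:

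| Control rate | 50% reduction | 40% reduction | 30% reduction |
|---|---|---|---|
| 5.7% (planned) | 69.9% | 46.9% | 26.5% |
| 10% (assumed) | 93.0% | 74.9% | 47.1% |
| 15% (assumed) | 99.1% | 91.6% | 67.2% |

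A true 40% reduction is therefore non-significant with probability 53%, 25% and 8% at the three rates. A higher composite rate moves the gap to smaller relative effects; it does not close it.

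**4. Can 3.6 points serve as the bound?** With identical arms of 675, the upper limit is 2.50 points at 38 events (5.6%), 3.23 at 68 (10.1%) and 3.61 at 88 (13.0%). From a control rate of about 13% upward, even a zero observed difference cannot exclude 3.6 points.

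**5. A Vanguard that closes early.** At the 300-patient maximum (150 per arm), exact power for 5.7% versus 2.1% is 24.7%; at 100 per arm it is 13.7%. Identical arms of 9 events in 150 give limits of ±5.7 points, so at these rates a null result could not exclude the design difference.

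**The case against.** Several points on the other side stand and limit the claim.

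- A reader might infer that the protocol sets a rule under which p>0.05 means no benefit. It does not. The sentence in section 1 is an impact statement and is comparative. Against trials of 177 and 150 patients and a pooled 885 from randomised trials, a null result in 1350 would indeed be stronger evidence. What remains is that the analysis plan neither defines null nor limits how it may be read.
- A reader might infer that a worthwhile benefit will be missed more often than not. That holds for a 40% reduction at a 5.7% control rate (53%), but not at an assumed 10% (25%) or 15% (8%). The composite rate may well exceed 5.7%, because section 2 accepts that stone debris and stents cause symptoms the endpoint counts.
- A reader might infer that a null Vanguard would count against prophylaxis. Neither section 1 nor section 4 says so. Nor would a failed Vanguard necessarily have 200 patients: that minimum belongs to meeting the targets, and six months may end the phase with fewer.
- A reader might infer that no effect estimate will appear. The plan says the outcomes will be reported, so arm rates should allow one to be derived. The gap is in pre-specification.
- The 38 versus 23 example is the extreme case. At the planned rate, 38 versus 30 already excludes 3.6 points.
- Which benefit would justify prophylaxis is a clinical judgement the documents do not make. That is a reason for the sponsor to state a bound; it does not justify leaving one out.

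**Conclusion.** The concern holds as a gap between the conclusion the protocol hopes to draw and the analysis it pre-specifies. The randomised comparison remains valid. What is unsupported is reading any non-significant result as evidence against routine prophylaxis: at the planned rate, such results range from one compatible with a 4.5-point benefit to one that rules out anything above 2.5 points, and Fisher's p-value does not say which has occurred.

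The size depends on the composite control rate, which the documents do not give. Power for a 40% reduction is 47% at 5.7% and 92% at an assumed 15%; for a 30% reduction it is 26.5% and 67%. These figures assume 675 patients per arm with observed outcomes and the same relative reduction across the whole composite. Counting lost patients as event-free would shrink the observed difference: with 10% lost in each arm, 3.6 points becomes 3.6 × 0.9 = 3.24.

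**What to change.** 1. In Statistical analysis, pre-specify the risk difference and risk ratio, each with a 95% CI, for the primary composite alongside Fisher's test.
2. State the reading rule: a non-significant result supports dropping routine prophylaxis only if the upper 95% limit for absolute benefit lies below a bound the sponsor sets in advance for the composite; otherwise it is inconclusive. The 3.6-point design difference is usable only if the composite control rate is near 5.7%.
3. Reword the impact sentence in section 1 to match.
4. In section 4, state that a Vanguard that closes early will report estimates with CIs and draw no conclusion on efficacy.

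This needs wording and two estimates from data already being collected, with no change to design, sample size or follow-up. The downside is that some null results will have to be called inconclusive.
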